8.1.2.3 Post-bronchodilator Spirometry

All participants must meet inclusion criterion 3 either by having documented historical reversibility or by demonstrating reversibility either at Visit 1 or Visit 2. Even if documented historical reversibility is available, the post-BD spirometry procedures must be performed at Visit 1 to categorize participants (establish baseline characteristic) prior to randomization. The documented historical reversibility must be recorded in the eCRF/spirometer prior to randomization.

The post-BD spirometry procedure should commence within 30 ± 15 minutes according to the regimen for reversibility testing outlined in Section [8.1.2.5](#) and [Figure 3](#).

8.1.2.4 Order of Administration

[figure not shown]
Order of administration of usual asthma controller medication and study intervention relative to scheduled pre and post-bronchodilator spiograms.

The participant's usual morning asthma controller therapy must not be given until after the initial pre-medication, pre-BD spirogram is complete for the reasons discussed above; usual asthma controller may be given after the post-BD spirogram.

8.1.2.5 Reversibility Test and Post-BD FEV₁ Assessment

The procedure described in this section refers to the reversibility testing at Visit 1 or Visit 2. Bronchodilatation can be induced using albuterol (90 µg metered dose), salbutamol (100 µg metered dose) or levalbuterol (45 µg metered dose) up to a maximum of 8 inhalations. It is highly recommended to use a spacer device for this procedure. The algorithm for reversibility testing is outlined in [Figure 3](#).

Figure 3 Reversibility Testing Algorithm

Abbreviations: BD=bronchodilator; FEV₁=forced expiratory volume in 1 second; SABA=short-acting β 2 agonists.

- 1 Verify with the participant that the medication restrictions to allow the reversibility assessment have been met (Section 6.5.2).
- 2 After a gentle and complete expiration, albuterol, salbutamol or levalbuterol is inhaled in one breath to total lung capacity from a spacer device. The breath is then held for 5 to 10 seconds before the participant exhales. Four separate inhalations are delivered at approximately 30 second intervals. Post-BD spirometry should be performed 15 to 20 minutes later.
- 3 If the participant has not met reversibility criteria, an additional 2 inhalations of albuterol, salbutamol, or levalbuterol can be administered as single inhalations, 30 seconds apart (for a total of 6 inhalations). Second post-BD spirometry should be performed 15 to 20 minutes later.

4 If the participant still has not met reversibility criteria, an additional 2 inhalations of albuterol, salbutamol, or levalbuterol can be administered as single inhalations, 30 seconds apart (for a total of 8 inhalations). Third post-BD spirometry should be performed 15 to 20 minutes later.

A lower total dose, eg, 2 inhalations instead of 4 in the first round of puffs can be used if there is a concern about any effect on the participant's heart rate, tremor, or safety. The bronchodilator algorithm can be stopped at any time once a participant has met reversibility criteria.

The highest pre and post-BD FEV₁ should be used to determine reversibility.

[figure not shown]
Reversibility is calculated as follows:

$$\% \text{ Reversibility} = \frac{(\text{post-BD FEV}_1 - \text{pre BD FEV}_1) \times 100}{\text{pre-BD FEV}_1}$$

[figure not shown]
8.1.2.6 Record Keeping

A signed and dated copy of the pre- and post- BD printout must be kept at the study center for source data verification. The printout must be marked with the study code, enrollment code, date and time of measurement, and visit number.

CCI

CCI

CCI

8.2 Safety Assessments

8.2.1 Physical Examinations

Physical examination will be performed at timepoints as specified in the SoA (Section 1.3).

Baseline data will be collected at Visit 1. Any new finding(s) or aggravated existing finding(s), judged as clinically significant by the investigator, will be reported as an AE as described in Section 8.3.

- A complete physical examination will be performed and include assessments of the following; general appearance, respiratory, cardiovascular, abdomen, skin, head and neck (including ears, eyes, nose, and throat), lymph nodes, thyroid, muscular-skeletal (including spine and extremities) and neurological systems.

- A brief physical examination will include, at a minimum, assessments of the general appearance, abdomen, cardiovascular, and respiratory system. For the brief physical examination only information on whether the assessment was performed or not is to be recorded.

8.2.2 Vital Signs

Pre-dose vital signs (pulse, blood pressure, respiration rate, and body temperature) are to be obtained in accordance with the SoA (Section 1.3).

Body temperature is to be recorded in degrees Fahrenheit/Celsius.

8.2.3 Local Electrocardiograms

An ECG will be performed at Visit 1 as specified in the SoA (Section 1.3).

A single 12-lead ECG will be taken in supine position, after the participant has been resting for at least 5 minutes. The assessment should be performed before interventions with the participant (eg, spirometry). Measurements will be performed on site supplied equipment.

A standard ECG with a recommended paper speed of 25 or 50 mm/second covering at least 6 sequential beats will be used. The investigator or authorized delegate will be responsible for the overall interpretation and determination of clinical significance of any potential ECG findings. In case of discrepancy between the investigator's interpretation and that provided by the ECG machine (if applicable), the investigator's interpretation takes precedence and should be noted on the printout and recorded in the eCRF. Two identical copies of the ECG will be produced, quality checked, and kept in case of further need for re-evaluation. The ECG printouts will be signed and dated by the investigator and stored at the study center.

ECG data and evaluation will be recorded in the eCRF.

8.2.4 Clinical Safety Laboratory Assessments

All CSP-required laboratory assessments, as defined in Table 9 for the determination of clinical chemistry, hematology, and urinalysis, must be conducted in accordance with the Laboratory Manual and the SoA (Section 1.3). Fasting before blood draw is recommended but not mandatory.

Additional safety samples (repeated or scheduled) may be collected if clinically indicated at the discretion of the investigator.

The clinical chemistry and hematology will be performed at a central laboratory. Urinalysis, theophylline level, and SARS-CoV-2 viral diagnostic test will be performed at a local laboratory at the investigator site. Sample tubes and sample sizes may vary depending on laboratory method used and routine practice at the site.

The investigator should make an assessment of the available results with regard to clinically relevant abnormalities. The laboratory results should be signed and dated and retained at site as source data for laboratory variables.

The following laboratory variables listed in Table 9 will be measured.

Table 9 Laboratory Safety Variables

Hematology / Hemostasis (whole blood)	Clinical Chemistry (serum or plasma)
B-Hemoglobin	S-ALP
B-Leukocyte count	S-ALT
B-Leukocyte differential count (absolute count) ^a	S-AST
B-Platelet count	S-Bilirubin, total
B-Hematocrit	S-BUN
B-MCV	S-Calcium, total
B-RBC count	S-Chloride
Urinalysis (dipstick) – local laboratory	S-Creatinine
U- Hemoglobin/Erythrocytes/Blood	S-Creatinine kinase (CK)
U-Protein/Albumin	S-CRP
U-Glucose	S-GGT
	S-Glucose
U-Microscopy and culture as required ^b	S-Phosphorus
	S-Potassium
SARS-CoV-2 (swab) – local laboratory	S-Sodium
SARS-CoV-2 viral test	S-Total cholesterol
	S-Uric acid
	S- Theophylline level (local laboratory) ^c

^a Eosinophil, basophil and monocyte counts will be redacted from the central laboratory reports, except for Visit 1 and Visit 3 (see Section 6.3.4).

^b Urine samples will be analyzed locally and sent to the central laboratory only for analysis when a positive dipstick result for any parameter is observed.

^c For participants on theophylline see Section 6.5.

Abbreviations: ALP=alkaline phosphatase; ALT=alanine aminotransferase; AST=aspartate aminotransferase; BUN=blood urea nitrogen; GGT=gamma glutamyl transpeptidase; HPF=high power field; MCV=mean corpuscular volume; RBC=red blood cell; SARS-CoV-2=severe acute respiratory syndrome coronavirus 2; WBC=white blood cell

NB. In case a participant shows an AST **or** ALT $\geq 3 \times$ ULN together with total bilirubin $\geq 2 \times$ ULN please refer to [Appendix D](#). Actions required in cases of increases in liver biochemistry and evaluation of Hy's Law, for further instructions.

8.2.5 Other Safety Assessments

8.2.5.1 Pregnancy Test

The following tests are applicable to female participants only and will be conducted at the timepoints specified in the SoA (Section 1.3).

- Serum β -HCG: To be done at screening Visit 1 only, for women of childbearing potential (analyzed at central laboratory).
- Urine pregnancy test: To be performed at the study center for women of childbearing potential at each treatment visit (before study intervention administration on Visit 3 to Visit 6) using a dipstick. A positive urine test result must be confirmed with serum β -HCG (analyzed at central laboratory).

8.2.5.2 Weight and Height

Weight and height will be measured, and BMI calculated in accordance with the SoA (Section 1.3).

The participant's weight will be recorded in pounds/kg; height will be recorded in inches/meters.

8.2.5.3 Serology

- Hepatitis B surface antigen and hepatitis C antibody
To be done at screening Visit 1 only (Section 1.3); test to be performed at central laboratory.
- HIV-1 and HIV-2 antibodies
To be done at screening Visit 1 only (Section 1.3); test to be performed at central laboratory.

Instructions for sample collection, processing, storage, and shipment can be found in the separate Laboratory Manual provided to the study centers.

8.2.5.4 SARS-CoV-2 Diagnostic Test

- Local viral testing to be performed at screening Visit 1 to confirm exclusion criterion 27 (Section 1.3).
- Results of local negative viral SARS-CoV-2 testing must be available and recorded in the eCRF before Visit 3.

Local COVID-19 viral test results must be recorded in the eCRF.

8.3 Adverse Events and Serious Adverse Events

The PI is responsible for ensuring that all staff involved in the study are familiar with the content of this section.

The definitions of an AE or SAE can be found in [Appendix E](#).

Adverse events will be reported by the participant (or, when appropriate, by a caregiver, surrogate, or the participant's legally authorized representative).

The investigator and any designees are responsible for detecting, documenting, and recording events that meet the definition of an AE.

8.3.1 Time Period and Frequency for Collecting AE and SAE Information

Adverse events will be collected from time of signature of the ICF, throughout the treatment period and including the follow-up period.

SAEs will be recorded from the time of signing of the informed consent form.

If the investigator becomes aware of an SAE with a suspected causal relationship to the study intervention that occurs after the end of the clinical study in a participant treated by him or her, the investigator shall, without undue delay, report the SAE to the sponsor.

8.3.2 Follow-up of AEs and SAEs

Any AEs that are unresolved at the participant's last AE assessment or other assessment/visit as appropriate in the study are followed up by the investigator for as long as medically indicated, but without further recording in the eCRF. AstraZeneca retains the right to request additional information for any participant with ongoing AE(s)/SAE(s) at the end of the study, if judged necessary.

Adverse event variables

The following variables will be collected for each AE;

- AE (verbatim)
- The date when the AE started and stopped
- Maximum intensity
- Whether the AE is serious or not
- Investigator causality rating against the study intervention(s) (yes or no)
- Action taken with regard to study intervention(s)
- AE caused participant's withdrawal from study (yes or no)
- Outcome

In addition, the following variables will be collected for SAEs:

- Date AE met criteria for SAE
- Date investigator became aware of SAE
- AE is serious due to
- Date of hospitalization
- Date of discharge
- Probable cause of death
- Date of death
- Autopsy performed
- Causality assessment in relation to study procedure(s)
- Causality assessment to other medication

8.3.3 Causality Collection

The investigator should assess causal relationship between study intervention and each AE, and answer ‘yes’ or ‘no’ to the question ‘Do you consider that there is a reasonable possibility that the event may have been caused by the study intervention?’

For SAEs, causal relationship should also be assessed for other medication and study procedures. Note that for SAEs that could be associated with any study procedure the causal relationship is implied as ‘yes’.

A guide to the interpretation of the causality question is found in [Appendix E](#) to the CSP.

8.3.4 Adverse Events Based on Signs and Symptoms

All AEs spontaneously reported by the participant or care provider or reported in response to the open question from the study site staff: ‘Have you/the child had any health problems since the previous visit/you were last asked?’, or revealed by observation will be collected and recorded in the eCRF. When collecting AEs, the recording of diagnoses is preferred (when possible) to recording a list of signs and symptoms. However, if a diagnosis is known and there are other signs or symptoms that are not generally part of the diagnosis, the diagnosis and each sign or symptom will be recorded separately.

8.3.5 Adverse Events Based on Examinations and Tests

The results from the CSP mandated laboratory tests and vital signs will be summarized in the CSR.

Deterioration as compared to baseline in CSP mandated laboratory values, vital signs and

other safety assessments should therefore only be reported as AEs if they fulfill any of the SAE criteria, are the reason for discontinuation of treatment with the study intervention or are considered to be clinically relevant as judged by the investigator (which may include but not limited to consideration as to whether treatment or non-planned visits were required or other action was taken with the study intervention, eg, dose adjustment or drug interruption).

If deterioration in a laboratory value/vital sign is associated with clinical signs and symptoms, the sign or symptom will be reported as an AE and the associated laboratory result/vital sign will be considered as additional information. Wherever possible the reporting investigator uses the clinical, rather than the laboratory term (eg, anemia versus low hemoglobin value). In the absence of clinical signs or symptoms, clinically relevant deteriorations in non-mandated parameters should be reported as AE(s).

Any new or aggravated clinically relevant abnormal medical finding at a physical examination as compared with the baseline assessment will be reported as an AE unless unequivocally related to the disease under study.

8.3.6 Adverse Events of Special Interest

An AESI is an event of scientific and medical interest towards improving the understanding of the study intervention. An AESI may be serious or non-serious. For this study, AESIs include:

- Anaphylactic reactions
- Immune complex disease (Type 3 hypersensitivity reactions)
- Malignancy
- Helminth infections
- Severe infections which are defined as:
 - SAEs or
 - Requiring treatment with systemic antiviral medications, intravenous antibiotics or medications for helminth parasitic infection or
 - Requiring a permanent discontinuation of study intervention
- Injection site reactions
- Opportunistic infections
- Guillain-Barré Syndrome

8.3.7 Hy's Law

Cases where a participant shows elevations in liver biochemistry may require further evaluation and occurrences of AST or ALT $\geq 3 \times$ ULN together with total bilirubin $\geq 2 \times$ ULN may need to be reported as SAEs. Please refer to [Appendix D](#) for further instruction on cases

of increases in liver biochemistry and evaluation of Hy's Law.

8.3.8 Disease Under Study

When collecting AEs, the recording of diagnoses is preferred, when possible, to recording a list of signs and symptoms. Asthma symptoms or signs, such as wheeze, cough, chest tightness, dyspnea, breathlessness and phlegm, will be recorded as AEs only when:

- The sign or symptom is serious according to definitions, see Appendix E 2.
- The participant discontinues the study due to the sign or symptom.
- The sign or symptom is new to the participant or not consistent with the participant's pre-existing asthma history (defined as within 1 year of Visit 1) as judged by the investigator.

CCI [REDACTED] should be recorded as an AE or SAE only if it fulfills any of the above criteria.

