2.3.1.2 Important Potential Risks

The mechanism of action of tezepelumab suggests potential inhibitory effects on immune responses mediated by Th2 cells, leading to the possibility of diminution of the host's protective response to infection.

Severe infections

Severe infections are defined as infections that are SAEs, require treatment with systemic antiviral medications, intravenous antibiotics or medications for helminth parasitic infection, or require permanent discontinuation of study intervention.

To mitigate the potential risk of severe infections eligibility criteria will exclude vulnerable participants, and included participants will be monitored for infection with complete blood counts, including differential white cell count throughout the study; and through standard AE/SAE reporting. Participants using immunosuppressive medication within 3 months prior to screening; who have a history of a known immunosuppressive disorder; who have a history

of clinically significant infection prior to screening; and who have known active or suspected tuberculosis either treated or untreated, will be excluded.

Parasitic infestation/infections

Tezepelumab may decrease the protective response to helminth infection by blockade of TSLP.

To decrease the risk of parasitic infestation or infection, participants who have a history of clinically significant infection prior to screening and at screening, and participants with untreated systemic helminth parasitic infections or those at significant increased risk of systemic helminth parasitic infestations will all be excluded.

Serious hypersensitivity/allergic reactions (including immune complex disease)

As with any large molecule therapeutics, administration of tezepelumab may result in systematic and/or local reactions. Systemic reactions to large molecule therapeutics can be IgE or non-IgE-mediated and are generally characterized by signs and symptoms such as skin rash, urticaria, pruritus, local or diffuse erythema, angioedema, fever, chills, cough, dyspnea, wheezing, bronchospasm, nausea/vomiting, diaphoresis, chest pain, tachycardia or bradycardia, and/or hypotension, which can all be severe or life-threatening. Effects typically occur during or within several hours after study intervention, but may be delayed.

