10 SUPPORTING DOCUMENTATION AND OPERATIONAL CONSIDERATIONS

Appendix A Anaphylaxis: Signs and Symptoms, Management

A 1 Introduction

As with any antibody, allergic reactions to dose administration are possible. The World Health Organization has categorized anaphylaxis into 2 subgroups, which are clinically indistinguishable: immunologic (IgE-mediated and non-IgE-mediated [eg, IgG and immune complex mediated]) and nonimmunologic (Johansson et al 2004). The clinical criteria for defining anaphylaxis for this study are listed in Appendix A 2. A guide to the signs and symptoms and management of acute anaphylaxis is provided in Appendix A 3. Appropriate drugs, such as epinephrine, antihistamines, corticosteroids, etc, and medical equipment to treat anaphylactic reactions must be immediately available at study sites, and study personnel should be trained to recognize and treat anaphylaxis according to local guidelines.

If an anaphylactic reaction occurs, a blood sample will be drawn from the participant as soon as possible after the event, at 60 minutes ± 30 minutes after the event, and at discharge for analysis of serum tryptase.

A 2 Clinical Criteria for Defining Anaphylaxis and Immune Complex Disease

Anaphylaxis

In adults, anaphylaxis is highly likely when any one of the following 3 criteria is fulfilled:

- 1 Acute onset of an illness (minutes to several hours) with involvement of the skin, mucosal tissue, or both (eg, generalized hives, pruritus or flushing, swollen lips-tongueuvula)
AND AT LEAST ONE OF THE FOLLOWING
 - (a) Respiratory compromise (eg, dyspnea, wheeze-bronchospasm, stridor, reduced PEF, hypoxemia).
 - (b) Reduced BP or associated symptoms of end-organ dysfunction (eg, hypotonia [collapse], syncope, incontinence).
- 2 Two or more of the following that occur rapidly after exposure to a likely allergen for that subject (minutes to several hours):
 - (a) Involvement of the skin-mucosal tissue (eg, generalized hives, itch-flush, swollen lips-tongue-uvula).
 - (b) Respiratory compromise (eg, dyspnea, wheeze-bronchospasm, stridor, reduced PEF, hypoxemia).
 - (c) Reduced BP or associated symptoms (eg, hypotonia [collapse], syncope, incontinence).
 - (d) Persistent gastrointestinal symptoms (eg, crampy abdominal pain, vomiting).

3 Reduced BP after exposure to known allergen for that subject (minutes to several hours):
Adults: systolic BP of less than 90 mm Hg or greater than 30% decrease from that subject's baseline.

Immune Complex Disease

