7.3 Appendix C: Adverse events of special interest

AESIs and related definitions based on MedDRA terms are not included in this SAP to facilitate their maintenance (e.g. management of MedDRA version changes), and for convenience in using them directly in SAS programming. These detailed definitions will be finalised by the study team prior to the primary database lock and provided together with the study datasets at the time of submission.

Anaphylactic reactions

Potential anaphylactic reactions will be defined on the basis of Sampson's criteria (see [Sampson et al 2006](#)) These will be identified using a modified Standardized MedDRA Query (SMQ), with additional constraints on the timing of the AE onset date relative to the timing of the injection.

Confirmed anaphylactic reactions will be those defined following medical review of the preferred terms identified as potential anaphylactic reactions, as well as any relevant supporting data.

Guillain-Barre syndrome

Guillain-Barre syndrome will be defined using an SMQ.

Helminth infections

Helminth infection will use an investigator-driven definition, i.e. will be directly determined from what is entered on the eCRF.

A subject will be considered to have this AESI if the subject has at least one preferred term where the dedicated Helminth Infection eCRF page was also completed for that event (linked by AE number), with AE onset date during the relevant study period for analysis.

Hypersensitivity reactions

Hypersensitivity reactions will be defined using a narrow SMQ excel file according to Integrated Summary of Safety (ISS) reporting.

Immune complex disease (Type III hypersensitivity reactions)

Immune complex disease will be defined using a single PT of “Type III immune complex mediated reaction”. Since this will already be covered by the general AE reporting by SOC/PT, separate summary tables will not be needed for this AESI.

Injection site reactions

Injection site reactions will use an investigator-driven definition, i.e. will be directly determined from what is entered on the eCRF.

A subject will be considered to have this AESI if the subject has at least one preferred term with AE onset date during the relevant study period for analysis, which has “AE category” on the Adverse Events eCRF page marked as “Injection Site Reaction”.

Malignancy

Malignancy will be defined on the basis of an SMQ.

Opportunistic infections

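### Protocol Section 8.3.8 has no condition for onset just after an injection, so a non-serious respiratory sign judged consistent with prior asthma need not reach the SAP's anaphylaxis or hypersensitivity searches

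*Protocol*

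**What the plan says.** **Recording rule.** Protocol Section 8.3.8: "Asthma symptoms or signs, such as wheeze, cough, chest tightness, dyspnea, breathlessness and phlegm, will be recorded as AEs only when" at least one of three conditions is met:

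- Seriousness: the event meets the SAE definition in Appendix E 2.
- Leaving the study: "The participant discontinues the study due to the sign or symptom". Stopping study intervention is not mentioned here.
- Novelty, which is left to the investigator's judgement: "The sign or symptom is new to the participant or not consistent with the participant's pre-existing asthma history". The history that counts is that within one year of Visit 1.

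**Risk and criteria.** Protocol Section 2.3.1.2 names serious hypersensitivity as an important potential risk. Its list of systemic reaction signs includes "angioedema, fever, chills, cough, dyspnea, wheezing, bronchospasm, nausea/vomiting". Appendix A 2 uses "Respiratory compromise (eg, dyspnea, wheeze-bronchospasm, stridor, reduced PEF, hypoxemia") as an element of anaphylaxis criteria 1 and 2. Section 8.3.6 makes anaphylactic reactions an AESI.

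**Analysis.** SAP Section 7.3 finds potential anaphylaxis by a modified SMQ "with additional constraints on the timing of the AE onset date relative to the timing of the injection". Confirmation is by medical review of the terms so identified, together with relevant supporting data. Hypersensitivity reactions, an AESI added by the SAP (Section 2), are also found by an SMQ. For AE timing, Section 8.3.2 of the protocol lists "The date when the AE started and stopped".

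**The concern.** The signs that 8.3.8 restricts are among those that the protocol treats as features of a systemic reaction to an injected biologic. The recording rule looks at seriousness, study discontinuation and consistency with asthma history, but not at when the sign began relative to an injection. Randomized participants must have asthma that is not well controlled (Section 5.1.2), so some will have wheeze, cough or dyspnea in their recent history, and the third condition may then not be met.

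At stake is the sensitivity of two AESI summaries. Where the investigator does not enter a diagnosis, the SMQ search is the back-up, and it can only work on signs that were entered as AEs.

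**Working it through.** The plan gives no figure on this point. The check sets the passages side by side and then makes one count.

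**Step 1. Take one sign through 8.3.8.** Suppose a wheeze begins during post-injection observation and is not serious, the participant stays in the study, and wheeze occurred in the past year.

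- Condition 1 (serious): not met.
- Condition 2 (leaves the study): not met. Section 7.1 separates stopping study intervention from withdrawing from the study, so stopping injections because of the wheeze would not meet it either.
- Condition 3 (new or inconsistent): met only if the investigator sees it that way. The text neither requires nor forbids weighing the onset after injection.

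Recording therefore rests on one unguided judgement.

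**Step 2. Look for another rule that would capture it.**

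| Section | What it does | Closes the gap? |
|---|---|---|
| 6.1.1.1, 6.2.1.3 | Observation after study intervention: at least 2 h at Visits 3 and 4, at least 1 h at later dosing visits | No AE recording rule for respiratory signs; 6.2.1.3 has one for injection site reactions |
| 6.2.2.2 | At least 15 minutes of observation after the vaccine | Same |
| 8.3.4 | General collection of reported or observed AEs; diagnosis preferred | Yes if a diagnosis is entered; otherwise 8.3.8 is the specific rule |
| 8.3.5 | Reports new or aggravated clinically relevant examination findings unless clearly due to asthma | Partly: a different test from 8.3.8, and for examination findings only |
| Appendix E 2 | Lists intensively treated allergic bronchospasm as an important medical event | Yes, through condition 1 |

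**Step 3. Follow it into the SAP.** A sign not entered as an AE has no preferred term and no onset date. It cannot contribute to the anaphylaxis search or the hypersensitivity search. It can reappear as supporting data only if some other recorded term has been flagged.

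**Step 4. Count the Appendix A 2 patterns that depend on the respiratory item.** Let S = skin/mucosa, R = respiratory, B = reduced blood pressure, G = gastrointestinal. Criterion 1: S and (R or B). Criterion 2: at least two of S, R, B, G. Criterion 3: B alone, after a known allergen. With R present there are 2 × 2 × 2 = 8 patterns. R alone does not qualify, which leaves 7. Remove R from each:

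| Pattern with R | Without R | Still qualifies? |
|---|---|---|
| S+R | S | No |
| R+G | G | No |
| R+B | B | Only through criterion 3 |
| S+R+B | S+B | Yes |
| S+R+G | S+G | Yes |
| R+B+G | B+G | Yes |
| S+R+B+G | S+B+G | Yes |

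So 2 of 7 are lost, or 3 of 7 if criterion 3 cannot be applied. This counts patterns under the clinical criteria. It is neither a case rate nor a test of the SMQ.

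**Step 5. Size of a timing condition.** On the four-dose schedule, minimum observation is 2 + 2 + 1 + 1 = 6 h after study intervention, plus 0.25 h after the vaccine: 6.25 h per participant. A condition covering each injection day and the next day would span 4 × 2 = 8 days (the vaccine shares a day with the fourth dose). Assume 3 symptom days a week, evenly spread, since one route in 5.1.2 is symptoms on more than 2 days a week. That gives 8 × 3/7 = 3.4 symptom days per such participant. If half of the 100 participants are of this kind (also an assumption), the total is 50 × 3.43, about 170.

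**The case against.** The strongest reply is that a clear case would be caught anyway. Urticaria with wheeze minutes after dosing fits the first anaphylaxis scenario in Section 6.1.1.1, where anaphylaxis is defined as a serious reaction, so condition 1 applies. Sections 8.3.4 and 8.3.8 prefer diagnoses to symptoms. Staff are trained to recognise anaphylaxis, participants are observed, and blood samples are prescribed after acute reactions. Section 8.3.8 is headed as concerning the disease under study, so a drug reaction arguably falls outside it. Exclusion criteria 6 and 19 remove people with anaphylaxis to a biologic or a known reaction to these products, so wheeze just after these injections should have no counterpart in the history. Section 5.1.2 can also be met without frequent current symptoms. The SAP adds a hypersensitivity AESI and allows supporting data at review.

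Most of this stands, and it confines the point to signs that are non-serious, undiagnosed and judged consistent with prior asthma. It does not remove the point: no text tells the investigator to treat post-injection onset as inconsistent with history, and both SAP searches need a recorded term.

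Three stronger readings are tempting, and the documents do not support them:

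- **That urticaria with an unrecorded wheeze would not be flagged.** SAP 7.3 keeps the detailed MedDRA definitions outside the SAP, so whether urticaria alone is picked up cannot be checked.
- **That date-only onset loses cases.** A day-level window is less specific but not less sensitive; medical review sorts the extra cases.
- **That the safety comparison is materially biased towards no difference.** Missed reactions caused by tezepelumab could only fall in that arm, but the recording rule is the same in both blinded arms, vaccine reactions can occur in either, and no rate is given from which to size an effect. Section 2.3.1 reports no causally related serious allergic or anaphylactic reactions in Phase 2 and 3.

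**Conclusion.** The point holds as a narrow gap in AE capture. A respiratory sign is lost to the SAP 7.3 searches when four things coincide: it starts after an injection, it is non-serious and does not lead to leaving the study, the investigator judges it consistent with the past year's asthma, and no diagnosis of anaphylaxis or hypersensitivity is entered. The 2 (or 3) of 7 patterns show where the respiratory sign decides whether Appendix A 2 is met; they do not say how often this will happen.

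This rests on reading 8.3.8 as governing any wheeze, cough or dyspnea in a participant with asthma, and on the redacted text containing no timing condition. The visible part of the sentence with a redacted subject in 8.3.8 refers back to the same three conditions. A reader should not infer that recognised anaphylaxis would go unreported. No hypothesis is tested (Section 9.1), and the primary antibody endpoints do not depend on AE recording. The change is worth making because it is cheap and concerns a named risk.

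**What to change.** Add a fourth recording condition to 8.3.8: the sign or symptom starts or worsens during the protocol's own observation period after study intervention or influenza vaccine, or occurs together with any other hypersensitivity sign listed in Section 2.3.1.2 or Appendix A. Reconcile 8.3.8 with the test that 8.3.5 applies to examination findings, so that one rule decides when a respiratory finding may be put down to asthma.

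The cost is one bullet, plus a few ordinary asthma symptoms near dosing recorded as AEs in both arms. Tying the condition to the observation period keeps that number small; the day-of-plus-day-after window sized in Step 5 would bring in much more background asthma. The change concerns data capture only and alters no treatment.

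Optional: an AE onset-time field for injection-day events. Dose time is recorded where applicable (Section 6.4), so this would let the SAP timing rule separate onset before from onset after the injection on the same day. It improves specificity, not sensitivity.
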